8.2 Safety Endpoints

NA. There are no primary or secondary safety endpoints in our study.

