7. Participants will be instructed to complete this survey exactly one week after transfusion and return it using the pre-addressed, pre-stamped envelope.
8. Site RAs will call participants using script (see Appendix D) to remind them to complete the QUALMS survey exactly one week after transfusion.
 - The window may increase up to one extra week to accommodate for circumstances where the patient is unable to complete the post-transfusion QUALMS (i.e., participant does not feel well or participant forgot).

PTQA Report

9. Once received, the second assessment will be scored and compared with the first, and both the patient and provider will be sent a report with the results. The QUALMS validation study suggested that a clinically meaningful difference on the instrument is between 5 and 10 points;¹² For this study:
 - A post-transfusion score that is within 5 points of the pre-transfusion score will indicate a stable QOL
 - A post-transfusion score that increases by 5 or more points will indicate a clinically significant improvement in QOL
 - A post-transfusion score that decreases by 5 or more points will indicate a clinically significant decline in QOL
10. In our report, we will include language that encourages patient and providers to use these results to inform their next transfusion decision, specifically suggesting that transfusion be halted or decreased in frequency if QOL has worsened.

**PROTOCOL TITLE: A New Paradigm of Transfusion Decision Support for Patients with MDS:
Using Peri-Transfusion Quality of Life Assessments (PTQAs)**

Secondary Outcomes Assessment

11. At 8 weeks post-transfusion, all participants will be sent a survey (Appendix B) to assess the utilization of the PTQA and patients' decisional regret, perceptions of care, and perceived stress.

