9.4 Data Collection

Data will be collected via medical record reviews, the QUALMS, and several other survey instruments.

Primary medical record review will include:

- Sociodemographic information
- Information regarding patients' MDS diagnosis, including IPSS-R score
- The number/frequency of transfusions prior to index transfusion (for transfusion-dependent patients)
- Hemoglobin level prior to index transfusion

Secondary medical record review will include:

- The presence of a second transfusion since index transfusion (for those who are starting transfusion)
- The number of red cell units used since index transfusion (for those who are transfusion-dependent)
- The number of hospitalizations since index transfusion
- The number of clinic visits since index transfusion

Survey instruments will include:

- The QUALMS to assess pre- and post-transfusion MDS-related QOL (see Appendix A)
- The Decision Regret Scale, "About Your Care" domain of prior DFCI survey, and the PSS-4 to assess secondary outcomes related to decisional regret, perception of care, and perceived stress (see Appendix B)

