12.0 Provisions to Monitor the Data to Ensure the Safety of Subjects

12.1 NA

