14.0 Risks to Subjects

14.1 As this is a survey study, we do not anticipate any risks due to study participation. The only foreseeable risk is potential emotional distress due to the nature of the questionnaires. If a participant becomes upset at any point, he/she will be referred to appropriate resources (e.g., social work, counseling). In the unlikely event that a patient is made upset or uncomfortable by the QUALMS survey, the study investigators will contact the treating physician to inform him or her of the patient's concerns.

14.2 *NA*

14.3 *NA*

14.4 *NA*

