APPENDIX C: PTQA Reports

PTQA Score Report (UNCHANGED SCORE)

Thank you for participating in the Peri-Transfusion Quality of Life Assessment (PTQA) study. The goal of this study is to determine whether the use of a quality of life questionnaire can help patients with MDS and their providers make better informed transfusion decisions. We hope that you will use the information in this PTQA score report to discuss future transfusion options with [Provider name].

What does your score mean?

Since your first and second scores are within 5 points of each other, your quality of life has **remained stable** after transfusion.

How should you use the score?

Given that your quality of life did not improve after your transfusion, we recommend that you discuss the benefits and risks of transfusion with your doctor.

Based on a focus group we conducted as part of our research, experts on myelodysplastic syndromes (MDS) agree that it is safe for patients with MDS to increase the time between transfusions or stop them altogether, as long as they are otherwise healthy, experience no significant benefit in their quality of life, and their hemoglobin level stays above 7.5 g/dL.

Your PTQA score suggests that you might consider limiting the number of transfusions you receive. However, there may be other explanations for your quality of life score. We encourage you to use this report to discuss future transfusion decisions with your doctor.

What are the next steps in the study?

The study team will contact you to complete your follow-up survey during the week of [date].

Questions or comments?

[figure not shown]
Please contact the [study team - provide site-specific study contact].

PROTOCOL TITLE: A New Paradigm of Transfusion Decision Support for Patients with MDS:
Using Peri-Transfusion Quality of Life Assessments (PTQAs)

PTQA Score Report (DECREASE)

Thank you for participating in the Peri-Transfusion Quality of Life Assessment (PTQA) study. The goal of this study is to determine whether the use of quality of life assessments can help patients with MDS and their providers make better informed transfusion decisions. We hope that you will use the information in this PTQA score report to discuss future transfusion options with [Provider name].

What does your score mean?

Since your second score is more than 5 points lower than your first, you have experienced a clinically significant **decrease** in your quality of life after transfusion.

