How should you use the score?

Given that your quality of life did not improve after your transfusion, we recommend that you discuss the benefits and risks of transfusion with your doctor.

Based on a focus group we conducted as part of our research, experts on myelodysplastic syndromes (MDS) agree that it is safe for patients with MDS to increase the time between transfusions or stop them altogether, as long as they are otherwise healthy, experience no significant benefit in their quality of life, and their hemoglobin level stays above 7.5 g/dL.

Your PTQA score suggests that you should consider limiting the number of transfusions you receive. However, there may be other explanations for this change in your quality of life score. We encourage you to use this report to discuss future transfusion decisions with your doctor.

What are the next steps in the study?

The study team will contact you to complete your follow-up survey during the week of [date].

Questions or comments?

[figure not shown]
Please contact the [study team - provide site-specific study contact].

PROTOCOL TITLE: A New Paradigm of Transfusion Decision Support for Patients with MDS:
Using Peri-Transfusion Quality of Life Assessments (PTQAs)

PTQA Score Report (INCREASE SCORE)

Thank you for participating in the Peri-Transfusion Quality of Life Assessment (PTQA) study. The goal of this study is to determine whether the use of quality of life assessments can help patients with MDS and their providers make better informed transfusion decisions. We hope that you will use the information in this PTQA score report to discuss future transfusion options with [Provider name].

What does your score mean?

Since your second score is more than 5 points higher than your first, you have experienced a clinically significant **increase** in your quality of life after transfusion.

How should you use the score?

Given that your score indicates a clinically significant increase in your quality of life, we do not recommend that you change your transfusion plan at this time. We encourage you and your provider to take changes in your quality of life into consideration when making transfusion decisions in the future.

What are the next steps in the study?

The study team will contact you to complete your follow-up survey during the week of [date].

Questions or comments?

Please contact the [study team - provide site-specific study contact].

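### The reports tie limiting transfusion to Hb staying above 7.5 g/dL, but no later Hb and no vital status is collected as an outcome, so a fall in transfusion use cannot be checked against that condition

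*Protocol*

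**What the plan says.** Section 8.2 is explicit: "There are no primary or secondary safety endpoints in our study". Section 12, on monitoring data for subject safety, is marked not applicable. Section 14.1 describes a survey study and says "we do not anticipate any risks due to study participation", apart from possible distress caused by the questionnaires.

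The study's output is nevertheless advice about transfusion. Section 9.2 describes the report as "specifically suggesting that transfusion be halted or decreased in frequency if QOL has worsened". In Appendix C the decreased-score report reads "Your PTQA score suggests that you should consider limiting the number of transfusions you receive", and the stable-score report makes a softer suggestion in the same direction. Both attach conditions: the patient must be otherwise healthy, "experience no significant benefit in their quality of life, and their hemoglobin level stays above 7.5 g/dL". The provider email in Appendix D repeats the Hb condition and adds the absence of end-organ effects.

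On data, the primary record review in 9.4 lists "Hemoglobin level prior to index transfusion". The secondary review covers second transfusion, red cell units, hospitalizations and clinic visits after index. It includes no later Hb and no vital status. The outcome lists in 1.1, 8.1, 11.1 and Appendix F do not include them either. Section 11.4 foresees deaths within the two months and includes those patients with the outcomes observed before death.

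**The concern.** Section 1.2 locates the hoped-for benefit mainly in less transfusion. The reports describe less transfusion as acceptable only under conditions, and the one numerical condition is an Hb level. The plan measures whether transfusion fell but not whether Hb then stayed above that level.

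The starting margin is small. Transfusion-naive patients enter as they approach 8.5 g/dL, which is 8.5 - 7.5 = 1.0 g/dL above the level the reports name.

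Death is a second gap. Under 11.4 a death can only reduce a patient's unit count or leave second transfusion at no. Both are the direction that 1.2 calls benefit. Without deaths reported for each group, a reader cannot tell fewer transfusions from less time in which to receive them.

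**Working it through.** **The plan's own figures (11.2).** These are not in dispute, but they fix the scale.
- Units: 30 v 30, 8.0 v 6.5, SD 2.0, two-sided 5% assumed. z = 1.5/(2.0 × √(2/30)) - 1.96 = 2.905 - 1.96 = 0.945, so power is 82.8% (stated 83%).
- Second transfusion: 100% v 70%, normal approximation with continuity correction. SE0 = √(2 × 0.85 × 0.15/30) = 0.0922 and SE1 = √(0.7 × 0.3/30) = 0.0837. Then (0.3 - 1/30 - 1.96 × 0.0922)/0.0837 = 1.03, so power is 84.8% (stated 85%).

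**Effect of the death rule on units.** The protocol gives no death rate, so the counts below are assumptions. At 8.0 units per 8 weeks, a death at mid-window forgoes half, and the group mean falls by 8.0 × 0.5/30 per death.

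| Mid-window deaths among 30 | Fall in mean units | Share of 1.5-unit target |
|---|---|---|
| 1 | 0.13 | 9% |
| 2 | 0.27 | 18% |
| 3 | 0.40 | 27% |
| 5 | 0.67 | 44% |

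Deaths among controls lower the control mean in the same way and so act in the opposite direction on the comparison. The net effect is unknown unless deaths are shown for both groups. A rate per week alive removes the mechanical part: 4 units over 4 weeks is 1.0 per week, the same as 8.0 over 8.

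**How well hospitalizations stand in.** With an assumed control mean of 0.2 to 0.5 admissions per 8 weeks (Poisson, 30 v 30, two-sided 5%, simulated), power to detect a doubling is about 29% to 62%.

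**What the added data could show.** With no events in n patients, the one-sided 95% upper bound is 1 - 0.05^(1/n): 9.5% for n = 30 and 4.9% for n = 60. The group advised to limit transfusion is smaller. If the 29% without improvement in the ambulatory oncology study cited in 2.3 applied here (an assumption: different population and measure), that is about 9 of 30 or 17 of 60, with bounds of about 28% and 16%.

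**Comparability of deaths.** Section 9.2 defines the index transfusion as one for which both questionnaires were completed, and the second is due one week later with up to one extra week. Section 11.1 requires both for the clinical outcomes. Evaluable participants have therefore survived to that questionnaire. No such requirement is stated for controls, so a raw count of deaths by group would favour PTQA.

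**The case against.** A reader might infer that the protocol would declare success on fewer transfusions even if patients were harmed. The documents do not support that. They contain no success rule, and this is a pilot whose first aim is feasibility. Hospitalizations stand beside transfusion use in the primary list and are compared with matched controls, so a rise in admissions would be reported next to any fall in units.

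Nor is hospitalization the only outcome able to show harm. Clinic visits are also primary, and the Decision Regret Scale includes an item on harm from the choice. That scale is descriptive and completed by participants only.

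It would also be wrong to say the study has no safety channel or safeguards. The monitoring plan in Appendix H provides for serious adverse event reports. Section 3.2 excludes patients with Hb below 7.5 g/dL, known CHF, unstable angina or Cr above 2. Section 22.1 says patients will be told they need not forgo transfusion, and the stable- and decreased-score reports send the patient to the doctor.

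All of this stands and narrows the point. It does not close the gap. Event reports are not an analysed outcome and cannot cover 2015-2017 controls. Admissions miss a low Hb managed without admission and a death outside hospital. Entry criteria say nothing about Hb after the report.

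A further objection is that lowest Hb cannot verify the whole condition, because the reports also require good general health and the email the absence of end-organ effects. That is correct: the added fields test only the Hb part.

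**Conclusion.** The point holds in this limited form. The protocol advises limiting transfusion subject to an Hb condition, declares no safety endpoints, and does not collect the Hb or vital status needed to check that condition or to interpret follow-up shortened by death. The consequence is confined to the two transfusion-use outcomes.

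The documents do not show that harm would occur or in which direction deaths would shift the comparison. The 0.13 units per mid-window death rests on the planned mean of 8.0 and a death halfway through the window. The 29% to 62% power rests on assumed admission rates.

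This is not a detail left to a SAP: 8.2 rules out safety endpoints and 9.4 fixes what is abstracted. It is an inexpensive improvement to interpretation and does not invalidate the study.

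**What to change.** - Add to the secondary record review in 9.4, for participants and matched controls over the 8 weeks after index: lowest Hb, any Hb below the level the reports name, number of Hb readings, and vital status with date of death.
- Amend 8.2 to list these as descriptive safety outcomes. Report them beside transfusion use by group and, for participants only, by report category.
- Require controls to have survived to the same landmark as evaluable participants, or state the bias in favour of PTQA that otherwise remains.
- Add transfusion units per week alive as a sensitivity analysis.

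The cost is a few fields in charts already being reviewed. The main weakness is that Hb is measured at clinical discretion: fewer visits give fewer readings and can make PTQA look safer, which is why the number of readings is needed. The data would be descriptive only, with wide bounds, widest within report categories. No dose, threshold or treatment rule is proposed.

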9.0 Procedures Involved

9.1 Study Design

We propose a prospective cohort pilot study where patients will complete the QUALMS survey before and after their first/next transfusion. We will aim to have two groups of study participants: (1) those that are approaching first transfusion and (2) those that are transfusion dependent (n=30 for each group).

9.2 Study Procedures

Please see study schema (Appendix C) for study flow.

Pre-Transfusion

- Once identified by Epic scheduling report, provider suggestion, or study-specific Epic Workbench report, eligible patients will be approached for consent discussion at an appointment with their provider.
 - Patients with Hb approaching 8.5 g/dL will be approached at an appointment prior to an upcoming transfusion.
 - Patients that are transfusion-dependent will be approached at an upcoming appointment with their provider or during a transfusion appointment.
- During this initial encounter, consenting participants will be given a study packet containing a paper copy of the QUALMS. Study participants will be instructed to fill out the survey on the day before their upcoming pRBC transfusion.

**PROTOCOL TITLE: A New Paradigm of Transfusion Decision Support for Patients with MDS:
Using Peri-Transfusion Quality of Life Assessments (PTQAs)**

3. Study participants will indicate whether they would like to receive PTQA reports in person, via mail, or via email.
4. Site RAs will call study participants using script (see Appendix D) on the day prior to an upcoming transfusion to remind them to complete the QUALMS and bring it with them to their transfusion.
5. Note: Index transfusion is defined as any upcoming transfusion appointment for which the participant has completed both the pre- and post-transfusion QUALMS questionnaires.
 - If a participant does not complete the pre-transfusion questionnaire for any reason (i.e., participant forgot to complete at home or forgot to bring in), then the RA may ask the participant to complete the questionnaire at home prior to a subsequent transfusion appointment. This subsequent transfusion will become the index transfusion.
 - If a participant does not complete the pre-transfusion QUALMS at home prior to the appointment and there are extenuating circumstances (i.e., participant does not regularly receive transfusions at the site), then the RA may ask the participant to complete the questionnaire in clinic before his/her planned index transfusion.

Post-Transfusion

6. On the day of transfusion, the site RA will collect the completed pre-transfusion QUALMS survey. Study participants will then receive a second paper copy of the QUALMS, along with a stamped envelope addressed to the appropriate site.
7. Participants will be instructed to complete this survey exactly one week after transfusion and return it using the pre-addressed, pre-stamped envelope.
8. Site RAs will call participants using script (see Appendix D) to remind them to complete the QUALMS survey exactly one week after transfusion.
 - The window may increase up to one extra week to accommodate for circumstances where the patient is unable to complete the post-transfusion QUALMS (i.e., participant does not feel well or participant forgot).

PTQA Report

9. Once received, the second assessment will be scored and compared with the first, and both the patient and provider will be sent a report with the results. The QUALMS validation study suggested that a clinically meaningful difference on the instrument is between 5 and 10 points;¹² For this study:
 - A post-transfusion score that is within 5 points of the pre-transfusion score will indicate a stable QOL
 - A post-transfusion score that increases by 5 or more points will indicate a clinically significant improvement in QOL
 - A post-transfusion score that decreases by 5 or more points will indicate a clinically significant decline in QOL
10. In our report, we will include language that encourages patient and providers to use these results to inform their next transfusion decision, specifically suggesting that transfusion be halted or decreased in frequency if QOL has worsened.

**PROTOCOL TITLE: A New Paradigm of Transfusion Decision Support for Patients with MDS:
Using Peri-Transfusion Quality of Life Assessments (PTQAs)**

Secondary Outcomes Assessment

11. At 8 weeks post-transfusion, all participants will be sent a survey (Appendix B) to assess the utilization of the PTQA and patients' decisional regret, perceptions of care, and perceived stress.

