8.0 Study Endpoints

8.1 Study Outcomes

Primary Endpoints

Subjects will be compared with historical controls (matched for transfusion group; IPSS-R; pre-transfusion Hb; and institution) seen between 2015 and 2017. For the transfusion-naïve, the primary outcome will be receipt of second transfusion (yes/no) within 8 weeks following the index transfusion. For the transfusion-dependent, the primary outcome will be defined as number of units pRBCs received within 8 weeks following the index transfusion. For both groups, we will also compare the number of hospitalizations and clinic visits during the 8 weeks after index transfusion (Table).

Secondary Endpoints

Secondary endpoints include decisional regret, perceptions of care, and perceived stress by the associated scales at two months post-transfusion (Table 1).

Table. Primary and Secondary Outcomes, Measured at Two Months after PTQA

Primary	Presence of second transfusion after PTQA (for those undergoing first transfusion) Number of red cell units used since PTQA (for transfusion-dependent) Number of hospitalizations since PTQA Number of clinic visits since PTQA
Secondary	Decisional Regret Decision Regret Scale. ³² 5-item scale provides indicator of health care decision regret; will be tailored to measure regret about transfusion decisions. Perceptions of Care “About Your Care” Domain of Prior DFCI Survey. We previously developed ³³ a 6-item domain based on the Consumer Assessment of Healthcare Providers and Systems Survey “health status” “access,” and “communication” domains. ³⁴ Perceived Stress PSS-4. ³⁵⁻³⁷ The PSS-4 was designed for use with patients with at least a junior high school education, and takes 3 minutes to complete. It contains four questions about feelings of control and overall stress, with simple response alternatives.

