11.0 Data Management and Confidentiality

11.1 Data Analysis Plan

Feasibility

Feasibility will be characterized by calculating (1) the proportion of enrolled patients out of all patients approached, and (2) the proportion of patients who completed both the pre- and post-transfusion QUALMS surveys out of all enrolled patients. A convenience sample of 60 evaluable patients will be enrolled to the study. To reach this goal, we will enroll 90 participants total, with the expectation that some patients will not be able to complete the study protocol, despite being eligible at the time of consent (e.g., do not end up requiring future transfusions). If the observed survey completion rate is 50% (i.e. 30/60), then this observed rate is consistent, with 95% confidence, with the true survey completion rate being as low as 38% or as high as 62%.

Clinical and Utilization Outcomes

To be assessed for clinical and utilization outcomes, participants must have completed a pre-transfusion QUALMS, received an index transfusion, and completed a post-transfusion QUALMS. Each of the 60 enrolled evaluable patients will be matched 1:1 to historical controls seen between 2015 and 2017, for a matched sample size of 120 patients total. Subjects will be matched for transfusion group, IPSS-R, pre-transfusion Hb, and institution). Comparative analyses will be conducted separately by transfusion group. For the transfusion-naive, the primary outcome will be receipt of second transfusion (yes/no) within two months following the first transfusion. For the transfusion-dependent, the primary outcome will be defined as number of units pRBCs received within two months following the next transfusion.

For both groups, we will also compare the number of hospitalizations and clinic visits two months after index transfusion (Table).

PTQA Utilization and Patient-Reported Outcomes

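### The index transfusion is defined by two completed QUALMS surveys, a condition no 2015-2017 control can meet, which leaves the roughly 30 transfusion-dependent controls without a fixed time zero

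*Protocol*

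**What the plan says.** **Definition.** Protocol 9.2 (Pre-Transfusion, step 5): "Index transfusion is defined as any upcoming transfusion appointment for which the participant has completed both the pre- and post-transfusion QUALMS questionnaires". If the pre-transfusion survey is missed, the RA may ask for it before a later appointment, and "This subsequent transfusion will become the index transfusion". The post-transfusion survey is due one week after transfusion, and "The window may increase up to one extra week to accommodate for circumstances where the patient is unable to complete the post-transfusion QUALMS".

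**Use.** In 8.1 the transfusion-dependent outcome is the "number of units pRBCs received within 8 weeks following the index transfusion". Second transfusion, hospitalizations and clinic visits run from the same index. Section 9.4 records hemoglobin before the index, and hemoglobin is a matching factor.

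**Comparator.** Section 8.1: "Subjects will be compared with historical controls (matched for transfusion group; IPSS-R; pre-transfusion Hb; and institution) seen between 2015 and 2017". Section 11.1: "Each of the 60 enrolled evaluable patients will be matched 1:1 to historical controls seen between 2015 and 2017".

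**Other anchors.** For the transfusion-naive, 11.1 says "the primary outcome will be receipt of second transfusion (yes/no) within two months following the first transfusion". For the transfusion-dependent it counts the "number of units pRBCs received within two months following the next transfusion".

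**Missing post-transfusion survey.** Section 11.1 requires both surveys for the clinical and utilization outcomes. Section 11.4 nevertheless plans to evaluate the outcomes of participants who never complete the second one.

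**The concern.** In a comparison with historical controls, both cohorts need a start of follow-up that is set by the same kind of rule. Here the start is a condition that only participants can satisfy, and it is confirmed for them only one to two weeks after the transfusion.

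A transfusion-dependent control may have several transfusions that meet the hemoglobin match, and the control mean depends on which one starts the 8 weeks. The units given afterwards are already in the same record, and nothing in the protocol fixes the choice before they are seen.

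The definition also builds in unequal conditions. A participant must be alive and able to complete a survey in the first one to two weeks of the 8-week window. A control need not be. At stake is the transfusion-dependent primary comparison, 30 versus 30, where the planned effect is 1.5 units.

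**Working it through.** **1. Can a control be given an index from the text?**

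| Section | Anchor | Applicable to a control? |
|---|---|---|
| 9.2 | Transfusion with both surveys completed | No |
| 8.1, 9.4 | Index transfusion | No, since it depends on 9.2 |
| 11.1, naive | First transfusion | Largely yes, if never transfused |
| 11.1, dependent | Next transfusion | No, since controls have no enrollment date |
| Appendix F | Index transfusion | No, since it depends on 9.2 |

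The other places that describe controls (1.1, 4.1, 23.2) give matching factors, years or numbers, but no index rule. The naive anchor is not fully aligned either: 3.2 admits previously transfused patients who have had no red cells for 8 weeks, and step 5 of 9.2 can move a participant's index past the first transfusion.

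**2. The plan's own power (11.2).** Inputs: 30 per group, means 8.0 and 6.5 units, SD 2.0, alpha 5% (taken as two-sided).

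- SE = 2.0 × √(2/30) = 0.516
- Noncentrality = 1.5 / 0.516 = 2.905
- Normal approximation: Φ(2.905 − 1.960) = 82.8%
- Two-sample t test, 58 df: 81.5%

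The stated 83% is reproduced. The problem is the start of follow-up, not the arithmetic.

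**3. How many candidate dates?** 11.2 implies 8.0 units per 8 weeks. Two units per transfusion at regular intervals is an assumption. It gives 4 transfusions per 8 weeks, or 0.5 per week. Dates with a full 8 weeks of follow-up = 0.5 × (weeks of record − 8):

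- 26 weeks: 0.5 × 18 = 9
- 52 weeks: 0.5 × 44 = 22

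At 1 unit per transfusion these double to 18 and 44. Matching on hemoglobin narrows the list but need not leave one date.

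**4. What a shift in the control mean would do** (t test, 58 df, critical value 2.002, SD held at 2.0; all shift sizes are assumptions).

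*Control mean raised, no true effect.* Chance of a significant result favoring PTQA, against 2.5% nominal:

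| Shift (units) | Noncentrality | False pro-PTQA rate |
|---|---|---|
| 0.25 | 0.25 / 0.516 = 0.484 | 6.9% |
| 0.5 | 0.5 / 0.516 = 0.968 | 15.7% |
| 1.0 | 1.0 / 0.516 = 1.936 | 47.8% |

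*Control mean lowered, true effect 1.5.* Suppose 10% of control index dates fell on a last transfusion with no units after it. The mean would be 0.9 × 8.0 + 0.1 × 0 = 7.2, a shift of 0.8. The visible contrast is 1.5 − 0.8 = 0.7, and the noncentrality is 0.7 / 0.516 = 1.356. Power is 26.5% (t) or 27.3% (normal), about 27%.

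**5. Scale.** As a worst case, always taking the higher of two windows moves the mean by 0.564 × 2.0 × √(1 − ρ). At an assumed within-patient correlation ρ of 0.75 this is 0.56 units. At 0.25 it is about 0.98. This bounds what selection could do and does not predict what will happen.

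**The case against.** **This belongs in the SAP.** A control index rule is often left there, and step 5 is a note within participant procedures. That would answer a bare omission. But 8.1 and 9.4 attach the outcomes and the matching hemoglobin to the term that step 5 defines, so the protocol fixes time zero in a form that fails for one side of the comparison. An SAP would have to replace that definition as well as add to it.

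**Section 11.1 supplies anchors.** This stands in part. A reader might infer that all 60 controls lack a time zero, and the document does not support that: the first transfusion can be found in the record of a never-transfused control. The open choice applies fully to the dependent group.

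**Matching and outcome data are reviewed separately.** Section 9.4 does list a primary and a secondary record review. A reader might infer that abstractors will pick dates with the outcomes in view. Nothing in the text says so. Equally, 9.4 promises neither an order nor blinding for controls.

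**The sizes are assumed.** This stands. Units per transfusion, the 10% share and every shift are assumptions. The planning mean of 8.0 may already include patients with few or no units. Very large counts of candidate dates, such as 74 over three years (0.5 × 148), need one control to be transfused regularly throughout 2015-2017, which the protocol does not say.

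**It is a pilot.** True, but the protocol names these comparisons as primary and powers them.

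**Conclusion.** The concern holds in limited form. The survey-based definition cannot be applied to any historical control, and the alternative wording in 11.1 does not rescue the roughly 30 transfusion-dependent controls. For never-transfused naive controls the gap is much smaller, although the anchors in 8.1 and 11.1 should still agree. The participants' index is not purely prospective, because it stands only once a survey completed one to two weeks later is in hand. Participants without that survey, whom 11.4 intends to evaluate, have no index under 9.2.

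The size and direction of any bias are unknown. The figures of about 16% false pro-PTQA findings (0.5 unit up) and about 27% power (0.8 unit down) are illustrations at SD 2.0 with 30 per group. A reader might take them as evidence that the comparison will be biased by an amount like the planned effect. The protocol does not show this. It shows only that no rule prevents it.

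**What to change.** Define the index in both cohorts from information available at the transfusion:

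- **Participants:** the transfusion for which the pre-transfusion QUALMS was completed, whether or not the post-transfusion survey is returned.
- **Naive controls:** the first outpatient red cell transfusion after at least 8 weeks without one.
- **Dependent controls:** one transfusion chosen by a pre-specified, outcome-blind rule, for example random selection among those that follow a transfusion in the prior 8 weeks and meet the hemoglobin match. Always taking the earliest qualifying date would favor controls early in dependence, whereas participants may enroll at any point.

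Lock the matched list and index dates before any post-index control data are abstracted. Reconcile 8.1, 9.2, 11.1 and 11.4 so that all use this one index, and state how a naive participant is handled when the index is not the first transfusion.

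The cost is about a paragraph of text, somewhat more abstraction work in a set order, and slightly fewer usable control dates. No extra patients or visits are needed.
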